## 11.6 Adverse Event/Adverse Drug Reaction Expectedness

An AE/ADR is considered unexpected when the nature, severity, or outcome of the AE/ADR is not consistent with the information provided in the Reference Safety Document (Summary of product characteristics for ZOF and NEB).

Identification Number: FORM-000050125

Previous Doc Number: CTWI10A

Version Number: 1.0, CURRENT

**Protocol Template** 

Sponsor: Menarini Pharmaceutical Study Code: MEIN/19/ZoNe-HYP/001

Protocol Version\_1 of 16/07/2020

#### 11.7 Serious Unexpected Adverse Drug Reaction

Any SAE judged by the Investigator or the Sponsor as drug-related (see Section 11.3) and considered as unexpected qualifies as a serious unexpected adverse drug reaction (SUSAR).

Suspected unexpected serious adverse drug reactions are subjected to expedited reporting, as specified in Section 11.10, as having a "Reasonable Possibility" of relationship with the IMP.

#### 11.8 Individual Case Safety Report

Format and content provided to describe one or several AEs or a disease experience that occur to an individual patient at a particular point of time.

## 11.9 Collection, Recording, and Reporting of AEs

At each visit the Investigator will collect and assess any AEs that have occurred in each patient since he/she had signed the informed consent.

Any laboratory test abnormality (newly occurring after the study treatment administration or worsening of previously known abnormalities) that the Investigator considers as clinically relevant: ie, values significantly above or under normal range or which require an intervention or diagnostic tests or may result in the study treatment discontinuation will be reported as an AE.

Any AE communicated by the patient or by the patient's relatives or delegates through phone calls, letters, or emails will also be collected and assessed.

The Investigator shall record on the respective eCRF AE recording pages/AE form any recognised AE identifying an individual case safety report (ICSR), both serious and nonserious, whether or not thought to be drug-related, observed in or reported by the patient (or relatives/delegates), specifying the judgement on the causal relationship with the study treatment.

Any available information and diagnostic measure (laboratory and instrumental tests, procedures, etc.) shall be recorded in and/or attached to the concerned eCRF pages/sections.

The Investigator is expected to record also any AE which was ongoing at the last treatment dose and a follow-up phone call should be made after 2 weeks from the last study visit.

Identification Number: FORM-000050125

Previous Doc Number: CTWI10A

Version Number: 1.0, CURRENT

#### **Protocol Template**

Sponsor: Menarini Pharmaceutical Study Code: MEIN/19/ZoNe-HYP/001

Protocol Version\_1 of 16/07/2020

In case AE was ongoing, the Investigator is expected to follow-up until the outcome of the AE has been determined.

The Investigator must report all the collected information on any ICSR including seriousness (whether or not thought to be related to the investigational drug), providing the concerned eCRF AE pages by alert e-mail, after the first knowledge of the occurrence of the case, to:

CRO Pharmacovigilance Officer: Will be reported through CRO's Pharmacovigilance group (ZoNe [contact]) for which its details will be provided via study guidelines

When relevant, the eCRF pages concerning medical history, concomitant medication, and laboratory tests should also be sent to the Sponsor by e-mail.

## 11.10 Management of Serious AEs (SAEs) Including Laboratory Abnormalities

## Reporting Duties of the Investigator

If the investigator becomes aware of a serious adverse event with a suspected causal relationship to the investigational medicinal product that occurs **after the end of the clinical trial** in a subject treated by him or her, the investigator shall, without undue delay, report the serious adverse event to the sponsor

The Investigator must report all the collected information on any serious ICSR (whether or not thought to be related to the investigational drug), as specified above, no later than 24 hours after the first knowledge of the occurrence of the case.

Any further information and supporting documentation that becomes available (copies of laboratory reports, tests, procedures, autopsy evidence of the cause of death, etc.) shall be provided no later than 24 hours after first knowledge, by the Investigator, to the CRO by alert e-mail, to be forwarded to the Sponsor.

The Investigator must also comply with the local applicable obligation(s) on the reporting of ADRs to the local concerned regulatory authority/EC.

Identification Number: FORM-000050125

Previous Doc Number:
CTWI10A

Version Number: 1.0, CURRENT

#### **Protocol Template**

Sponsor: Menarini Pharmaceutical Study Code: MEIN/19/ZoNe-HYP/001

Protocol Version\_1 of 16/07/2020

#### **Reporting Duties of the Sponsor**

The Sponsor shall ensure that all relevant information about any SUSAR, is expeditiously reported to the competent authorities and ECs as required, with these deadlines after the first knowledge, intended as the day when the CRO receives the notification of the SUSAR:

- Fatal and life-threatening unexpected cases, no later than 7 days
- Other unexpected serious cases, no later than 15 days

The Sponsor shall ensure that all relevant information and supporting documentation that subsequently becomes available, is also expeditiously reported as follow-up information according to the above-mentioned deadlines.

Furthermore, the following safety issues will be patented to expedited management for the identification of possible necessary actions:

- SAEs associated with the trial procedures
- Potential clinically significant findings emerging from non-clinical studies
- An anticipated end or suspension for safety reasons of another trial with the same study treatment.

When appropriate and applicable, the Sponsor will arrange for adequate information to be communicated to the Investigators.

For trials in high morbidity and/or mortality disease, where the efficacy endpoint could also be a serious unexpected ADR or when a fatal or other serious outcome is the primary efficacy endpoint, agreement with the competent authority will be reached to treat the SAE as disease-related and not subject to expedited reporting.

#### 11.11 Management of Nonserious AEs Including Laboratory Abnormalities

#### **Reporting Duties of the Investigator**

The Investigator must report all the collected information on any NSAE ICSR (whether or not thought to be related to the investigational drug), as specified above, no later than 5 calendar days after the first knowledge of the occurrence of the case.

Identification Number: FORM-000050125

Previous Doc Number:
CTWI10A

Version Number: 1.0, CURRENT

#### **Protocol Template**

Sponsor: Menarini Pharmaceutical Study Code: MEIN/19/ZoNe-HYP/001

Protocol Version\_1 of 16/07/2020

Any further information and supporting documentation that become available (copies of laboratory reports, tests, procedures, etc.) shall be provided **no later than 24 hours** after the Investigator first becomes aware, to the CRO by e-mail or fax, to be forwarded to the Sponsor.

## 11.12 Management of Any Laboratory Abnormality

Any laboratory test abnormality which is considered by the Investigator as an AE, is to be managed as detailed above (refer to Section 10.2). However, all "out of range" values should be collected and reviewed periodically (modality to be established) by the CRO and the Sponsor.

## 11.13 Management of Pregnancy Exposure Cases

The Investigator is expected to record in the provided form any case of pregnancy exposure occurring in a female patient or in a male patient's partner during the treatment, sending it within 5 days after being made aware of the pregnancy, to the CRO by e-mail or fax, to be forwarded to the Sponsor.

The Investigator is requested to follow each case of pregnancy exposure until the outcome.

If the pregnancy results in an abnormal outcome, this will be recorded in the eCRF as an SAE and managed as described above.

Eligibility of a woman of childbearing potential (WOCBP) will be considered as described in Section 8.1. A woman is considered fertile following menarche and until becoming postmenopausal unless permanently sterile as described below.

Women in the following categories are not considered WOCBP if:

- Premenarchal
- Premenopausal female with one of the following:
  - Documented hysterectomy.
  - Documented bilateral salpingectomy.
  - Documented bilateral oophorectomy.

Note: Documentation can come from the study center personnel's: review of the patient's medical records, medical examination, or medical history interview.

Identification Number: FORM-000050125

Previous Doc Number:
CTWI10A

Version Number: 1.0, CURRENT

#### **Protocol Template**

Sponsor: Menarini Pharmaceutical Study Code: MEIN/19/ZoNe-HYP/001

Protocol Version\_1 of 16/07/2020

Postmenopausal female: A postmenopausal state is defined as no menses for 12 months without an alternative medical cause. A high follicle stimulating hormone (FSH) level to 30 mIU/mL or higher may be used to confirm a postmenopausal state in women not using hormonal contraception or hormonal replacement therapy (HRT). However, in the absence of 12 months of amenorrhea, a single FSH measurement is insufficient. Females on HRT and whose menopausal status is in doubt will be required to use one of the non-estrogen hormonal highly effective contraception methods if they wish to continue their HRT during the study. Otherwise, they must discontinue HRT to allow confirmation of postmenopausal status before study enrolment.

#### 12. WITHDRAWAL CRITERIA

#### Withdrawal of monotherapies or the study drug

Withdrawal from the monotherapies or study drug refers to any patient who does not receive the complete course, ie, when no further planned dose is administered from the date of withdrawal. A patient withdrawn from the monotherapies or study drug may continue further study procedures (safety) planned in the study protocol, as deemed appropriate by the Investigator once the safety of the patient is recovered/reassured.

A patient's study drug or monotherapies may be discontinued for any of the reasons below. In addition to the scheduled visits, patient who have been withdrawn from study drug or monotherapies may also undergo additional medical follow-up at the discretion of the Investigator.

- Any AE, which required treatment termination according to the Investigator's judgement
- Clinically significant intercurrent illness or laboratory results which could compromise the safety of the patient or the scientific value of the study
- Investigator deems it to be in the best interest of the patient to discontinue
- Requirement to use prohibited medication that could compromise the safety of the patient or the scientific value of the study

Identification Number: FORM-000050125

Previous Doc Number: CTWI10A

Version Number: 1.0, CURRENT

#### **Protocol Template**

Sponsor: Menarini Pharmaceutical Study Code: MEIN/19/ZoNe-HYP/001

Protocol Version\_1 of 16/07/2020

## Withdrawal of patient from the study

The patient may withdraw from the study at any time without explanation, without losing the right to future medical care. The participation of the patient may, at any moment, be terminated by the Investigator, if considered appropriate.

A patient can be withdrawn during the study for any of the following reasons:

- Any AE, which required treatment and study termination for the patient according to the Investigator's judgement
- Abnormal renal function or liver enzyme parameters as described in Section 10.2
- Patient becomes pregnant during the study
- Request of the patient (without giving any reason)
- Investigator deems it to be in the best interest of the patient to discontinue
- Failure to adequately comply with the dosing, evaluations, or other requirements of the study
- If the patient meets an exclusion criterion (newly developed or not previously recognized) that precludes further study participation
- Use of any prohibited medication (eg, concomitant use of aliskiren-containing products and ACE-i with sacubitril/valsartan or any other drug as specified per SmPCs of ZOF or NEB) that in the opinion of the Investigator or Sponsor necessitates the patient being withdrawn

The reason for the withdrawal of monotherapies or study drug, or withdrawal from the study must be well documented in the eCRF page and should capture the date and the specific underlying reason for discontinuation of study treatment or patient discontinuation/withdrawal.

Patients who discontinue from the study early will be asked, anyway, to complete all the assessments of Visit 3. Patients may discontinue the study product, but remain in the study for follow-up, especially for safety study endpoints (if applicable).

If a patient has been discontinued/withdrawn due to an AE, the Investigator must immediately notify the relevant pharmacovigilance contact (see Section 11.9) and should be followed-up until

Identification Number: FORM-000050125

Previous Doc Number:
CTWI10A

Version Number: 1.0, CURRENT

#### **Protocol Template**

Sponsor: Menarini Pharmaceutical Study Code: MEIN/19/ZoNe-HYP/001

Protocol Version\_1 of 16/07/2020

the AE is resolved or the Investigator deems further observations or examinations as no longer medically indicated.

## 13. LOST TO FOLLOW-UP

A patient will be considered lost to follow-up if he or she fails to return for the scheduled visits and is unable to be contacted by the study site staff.

The site will attempt to contact the patient and reschedule the missed visit. The site will also counsel the patient on the importance of maintaining the assigned visit schedule and ascertain if the patient wishes to and/or should continue in the study.

Before a patient is deemed lost to follow-up, the Investigator, or designee will make every effort to regain contact with the patient. These contact attempts should be documented in the patient's medical record or study file.

#### 14. STATISTICS

#### 14.1 Statistical Methods (Blinding and Randomization)

This is an open-label study. In this study all the patients are receiving monotherapy in the run-in period and combination therapy at the study treatment phase and no randomization is required.

#### 14.2 Determination of Sample Size

Considering a screen failure and a drop-out rate of 25% from Visit 1 and Visit 3, the number of patients to be screened is 290. Two-hundred and sixteen with uncontrolled hypertension, are planned to be included at Screening in the assessment period lasting for 8 weeks. A total sample size of 216 patients is required to achieve 90% power at 5% significance level assuming a difference in mean DBP from baseline to 8 weeks of 4 mmHg and a standard deviation (SD) for this difference of 10 mmHg. The mean change in DBP for null hypothesis is set at 2 mmHg.

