### **Protocol Template**

Sponsor: Menarini Pharmaceutical Study Code: MEIN/19/ZoNe-HYP/001

Protocol Version\_1 of 16/07/2020

The primary endpoint will be assessed before and after assessment period at Week 8, by a paired t-test using the ITT population and the Per protocol (PP) population. All other secondary endpoints will be assessed before (Week 0) and after treatment (at Week 8).

Statistical Assumptions

A total sample size of 216 patients is required to achieve 90% power at a 5% significance level assuming a difference in mean DBP from baseline to 8 weeks of 4 mmHg and a standard deviation (SD) for this difference of 10 mmHg. The mean change in DBP for the null hypothesis is set equal to 2 mmHg.

Identification Number: FORM-000050125

Previous Doc Number: CTWI10A

Version Number: 1.0, CURRENT

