#### 14.5.2 Primary (efficacy) Analysis

The primary efficacy analysis will be conducted on the intent-to-treat (ITT) population. The interpretation of results will be based on ITT population. The PP population will be used to assess the robustness of the results obtained using the ITT population.

The primary endpoint is the mean change from baseline in sitting DBP at Week 8 (Visit 3) for patients who are receiving combination therapy.

The statistical hypothesis will be defined as below:

H0: There is no change in the sitting DBP prior or post combination therapy

H₁: There is a difference in the sitting DBP prior or post combination therapy

Identification Number: FORM-000050125

Previous Doc Number:
CTWI10A

Version Number: 1.0, CURRENT

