### **6.5.** STATISTICAL TESTS

The default significant level will be (5%); confidence intervals will be 95% and all tests will be two-sided, unless otherwise specified in the description of the analyses.

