#### **6.6.** COMMON CALCULATIONS

For quantitative measurements, change from baseline will be calculated as:

• Test Value at Visit X – Baseline Value

And for change from Visit 1 will be calculated as:

• Test Value at Visit X – Visit 1 Value

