#### 16.1.3. PRIMARY ANALYSIS OF PRIMARY EFFICACY VARIABLE

The primary objective of this study is to test the hypothesis that

- H0: There is no change in the sitting DBP prior or post combination therapy
- H1: There is a difference in the sitting DBP prior or post combination therapy.

The primary efficacy analysis will be performed for the ITT population. The above hypothesis will be tested as following-

• Change from baseline in sitting DBP from prior and post combination therapy will be compared using paired t-test. The p-value will be presented using paired t-test.

Document: \\ieedc-vnasc01\BIOSdata\Menarini\NebZof\KZA41200\Biostatistics\Documentation\SAP

Author: [name] Version Number: Final V1.0

Version Date: [14Dec2021]

Template No.: CS\_TP\_BS016 Revision 6 Reference: CS\_WI\_BS005

Page 26 of 37

- The primary endpoint will be presented in a descriptive manner using n, mean, median, SD, Q1, Q3, minimum and maximum.
- Assumption of normality will be investigated using Wilk-Shapiro test. If violation is observed, then paired ttest will be replaced by Wilcoxon signed rank test.

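### The 90% power quoted for 216 patients belongs to a one-sided 5% test against 2 mmHg, but the planned primary test is two-sided against no change; 216 is also used for both entrants and completers

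*Protocol*

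**What the plan says.** **Sample size.** Protocol 14.2 states: "A total sample size of 216 patients is required to achieve 90% power at 5% significance level". The assumed mean change in DBP over 8 weeks is 4 mmHg with an SD of 10 mmHg, and "The mean change in DBP for null hypothesis is set at 2 mmHg". The synopsis (Statistical Assumptions) gives the same figures: "The mean change in DBP for the null hypothesis is set equal to 2 mmHg". Neither place says whether the 5% is one-sided or two-sided.

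**Primary test.** Protocol 14.5.2 gives the null hypothesis as "There is no change in the sitting DBP prior or post combination therapy", and SAP 16.1.3 repeats it. The alternative has no direction: "There is a difference in the sitting DBP prior or post combination therapy". The test is a paired t-test, replaced by the Wilcoxon signed rank test if normality is rejected. SAP 6.5 sets a 5% level and adds that "all tests will be two-sided, unless otherwise specified in the description of the analyses"; SAP 16.1.3 specifies nothing different. The 2 mmHg null appears in neither analysis section, and SAP 3.3, which lists changes from the protocol, does not mention it.

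**What 216 counts.** Protocol 14.2 says: "Two-hundred and sixteen with uncontrolled hypertension, are planned to be included at Screening in the assessment period lasting for 8 weeks". The synopsis, protocol Section 7 and SAP 3.1 instead give 216 as the approximate number completing the study. Section 7 also caps Visit 2 entry at 110 patients per run-in drug. Under SAP 3.3 and 7.3 the primary analysis uses observed data, with no imputation.

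**The concern.** The null value and the sidedness determine what a positive trial means. From protocol 14.2, a reader would expect success to show a fall in DBP beyond 2 mmHg, with a 10% risk of missing a true 4 mmHg fall. The analysis sections require evidence only of a change from zero. The two parts of the plan therefore describe different claims with different error risks, and the trial could be reported as positive without meeting the hypothesis it was sized on.

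This matters in a single-group, open-label trial. Patients enter because their pressure is still uncontrolled at Visit 2, and Visit 2 is also the baseline. A test against zero is easy to pass in that setting, so a non-zero null is a material part of the design. The documents do not explain why 2 mmHg was chosen.

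The double use of 216 adds a second uncertainty. With no imputation, each missing Week 8 value reduces the analysed number, so the power depends on whether 216 is counted before or after losses.

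**Working it through.** **Inputs.** n = 216, power 90%, level 5%, true change 4 mmHg, SD 10 mmHg, null 2 mmHg (protocol 14.2 and synopsis); null of no change (protocol 14.5.2, SAP 16.1.3); two-sided (SAP 6.5); 290 screened, 25% loss (protocol 14.2); cap 2 × 110 = 220 (protocol 7). I read the 4 and the 2 as falls.

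**Formulas.** The test is one-sample on the within-patient change, with d the distance between the true change and the null.
- Approximate size: n = (SD × (z_α + z_power) / d)².
- Exact power: noncentral t with n − 1 degrees of freedom and noncentrality d√n / SD.

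**Step 1: reproduce the plan's figure.** d = 4 − 2 = 2, one-sided 5%.
- n = (10 × (1.645 + 1.282) / 2)² = 214.1, so 215 by the normal approximation. The exact calculation gives 216.
- Exact power at 216 is 90.07%. The stated figure reproduces.

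**Step 2: the same null, two-sided.**
- n = (10 × (1.960 + 1.282) / 2)² = 262.7, so 263 by the normal approximation and 265 exactly.
- Exact power at 216 is 83.3%.

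**Step 3: the test as written.** d = 4 − 0 = 4, two-sided.
- n = (10 × (1.960 + 1.282) / 4)² = 65.7, so 66 by the normal approximation and 68 exactly.
- Noncentrality at 216 is 0.4 × √216 = 5.88, and exact power is 99.995%.

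| Test at 5% | Power at 216 | n for 90% | Smallest significant observed fall at n = 216 |
|---|---|---|---|
| One-sided, null 2 | 90.07% | 216 | 3.12 mmHg |
| Two-sided, null 2 | 83.3% | 265 | 3.34 mmHg |
| Two-sided, null 0 (as planned) | 99.995% | 68 | 1.34 mmHg |

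The last column takes the observed SD as 10. Two-sided, t(0.975, 215) × 10/√216 = 1.341, and adding 2 gives 3.341.

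**Step 4: a true fall of exactly 2 mmHg.** Tested two-sided against 0, d = 2, so the planned test rejects in 83.3% of trials. In that situation the sample-size null is true.

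**Step 5: what 216 counts.**
- 216/0.75 = 288, and 290 × 0.75 = 217.5. The 25% runs from Visit 1 to Visit 3, so the screening arithmetic fits completers.
- With at most 220 entrants, 216 completers leaves room for 4 losses: 4/220 = 1.8%.
- The documents give no loss rate after Visit 2. The rates below are assumptions, applied to 220 entrants.

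| Assumed loss | Evaluable | Two-sided power, null 2 | Two-sided power, null 0 |
|---|---|---|---|
| 5% | 209 | 82.1% | 99.993% |
| 10% | 198 | 80.0% | 99.986% |
| 15% | 187 | 77.7% | 99.975% |

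**The case against.** The strongest reply is that the arithmetic is not wrong: 216 follows from the stated inputs on a one-sided reading, and protocol 14.2 does not exclude that reading. The primary objective, endpoint, hypotheses and estimand all omit a 2 mmHg margin, so the sample-size sentence is the outlier, and for the written test 216 is more than enough. All of this stands. The fault is an inconsistency between sections, and the trial is not underpowered for the hypothesis it states. But the consistency of the other sections does not make 90% the power of the planned test, and a one-sided reading conflicts with the non-directional alternative and with SAP 6.5.

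A second route also reaches 216: a one-sided 5% comparison of two independent groups, difference 4 and SD 10, needs 108 per group. It drops the stated 2 mmHg null, does not match a paired single-group analysis, and is itself one-sided.

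On entrants and completers, the screening arithmetic and three of the four places favour completers, and the contrary sentence is awkwardly worded. The ambiguity hardly affects power against 0 and matters mainly if 2 mmHg is adopted. It is a secondary point, but the 220 cap still leaves almost no allowance for losses.

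Finally, SAP Section 1 cites a protocol addendum of 29 October 2020 that was not available for this review. It could bear on the sample-size text, although SAP 3.1 still repeats 290 and 216.

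**Conclusion.** The concern holds. Among one-sample tests with the plan's own inputs, 216 patients give 90% power only one-sided at 5% against 2 mmHg. The planned two-sided test has 99.995% power against 0, and a two-sided test against 2 mmHg would have 83.3%. The quoted 90% therefore describes neither the claim nor the risk of the primary analysis.

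The main consequence is for interpretation: the observed fall needed for success is 1.34 mmHg as planned, against 3.34 mmHg for a two-sided test of the sample-size null. The meaning of 216 also needs settling, since 216 completers from at most 220 entrants tolerates a 1.8% loss.

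These figures rest on the plan's SD of 10 and true change of 4 mmHg, on the paired t-test rather than the Wilcoxon fallback, and, for the loss scenarios only, on assumed loss rates.

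**What to change.** 1. **State one null value** in protocol 14.2, the synopsis, protocol 14.5.2 and SAP 16.1.3.
   - If 2 mmHg is the intended margin, test the mean change against it in both the paired t-test and the Wilcoxon fallback. SAP 6.6 defines change as "Test Value at Visit X – Baseline Value", so a fall is negative: the null is −2, and success in the t-test is an upper 95% confidence limit below −2.
   - If 0 is intended, remove the 2 mmHg null from 14.2 and the synopsis.
2. **State the sidedness in 14.2 and restate the power to match.** For 216 evaluable patients, true change 4 and SD 10, two-sided 5%: 83% against 2 mmHg, or over 99.9% against 0. A declared one-sided 5% test against 2 mmHg would keep 90%, but it must be written into 14.5.2 and SAP 16.1.3 as an exception to SAP 6.5, with a directional alternative.
3. **Say whether 216 means entrants or patients with Week 8 data**, and give the power at the number expected to be evaluable from at most 220 entrants.

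**Cost.** These are text changes and need no extra patients, provided 83% is accepted if the two-sided 2 mmHg test is chosen; restoring 90% there would take 265 evaluable patients, above the cap. Carrying 2 mmHg into the analysis changes the primary analysis, so protocol 14.7 requires a substantial amendment, and the observed fall needed rises from 1.34 to 3.34 mmHg (3.12 one-sided). Keeping 0 corrects only the sample-size text, but the plan then gives no basis for claiming a fall beyond 2 mmHg.
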